11.1.4 Treatment Period (21-day cycles)

11.1.5 Every Cycle: Day 1 ± 3 days (except Cycle1)

Day 1 pre-dose assessment do not need to be repeated if being done same day as screening. If the same assessments are being used for both screening and day 1, the data should be entered at screening in the database.

- ECOG performance status
- Serum chemistry as detailed above (11.1.2)
- LDH, uric acid and phosphorous only for cycle 1
- CBC with differential
- Physical examination
- Vital signs and weight
- Concomitant medication documentation including over the counter medication and supplements
- Adverse event documentation starting with cycle 2

11.1.6 Cycle #4 and #10 day 15 ± 5 days

- CT neck, chest, abdomen and pelvis with IV and oral contrast. Neck CT can be omitted at the discretion of the investigator if there was no involvement seen at baseline.

11.1.7 The treatment will be continued until disease progression, unacceptable toxicity, stem cell transplantation or at physician discretion. If a patient has completed 17 cycles, the treating physician can determine if to continue or discontinue treatment in event there is no disease progression or unacceptable toxicity. Patients who have completed 17 cycles of treatment can continue on the protocol at the discretion of the treating physician until disease progression or unacceptable toxicity. For patients continuing beyond 17 cycles, CT neck, chest, abdomen and pelvis with IV and oral contrast will be done every 6 months ± 2 weeks as long as they are receiving study treatment. Neck CT can be omitted at the discretion of the investigator if there was no involvement seen at baseline. For treatment schedule please refer to section 11.1.5.

11.2 End of Study Treatment Visit

End of study visit will be conducted within 30-45 days of last cycle of therapy

- Physical Examination
- Vital signs
- Height and weight
- Concomitant medication documentation, including over the counter medication and supplements
- CBC with differential
- Serum chemistry panel as mentioned above
- LDH
- Pregnancy test for females of childbearing potential
- ECOG performance status (not required if patient has disease progression)
- Adverse event evaluation

- Diagnostic CT of neck, chest, abdomen, pelvis with IV and oral contrast and PET scan to be done between 30-45 days after the last cycle of therapy. Neck CT can be omitted at the discretion of the investigator if there was no involvement at baseline. If unable to obtain both CT and PET scan due to insurance restrictions, either CT or PET are acceptable, but PET scan is preferred
 - For patients coming off treatment due to disease progression, scans are only required, if the last scan within 60 days did not show disease progression. If the patient had a scan within the last 60 days that document progression, no further scans are needed.
- BM biopsy to be repeated between 30-45 days after the last cycle of therapy if it was positive prior to start of the study drug.
 - BM biopsy may be omitted for patients who are coming off treatment due to disease progression.

11.3 Duration of Follow Up

As stated in section 6.7.2 after completion of the study the subjects will be followed for a total of 3 years. The follow up visits will be done at 6, 12, 24 and 36 months after the last cycle of therapy and will include:

- Physical Examination
- Vital signs, height, and weight
- CBC with differential
- Serum chemistry panel as mentioned above
- LDH
- ECOG performance status
- Adverse events evaluation (only the adverse events attributed to the study drug)
- CT scans - neck, chest, abdomen and pelvis with IV and oral contrast to be done at 6, 12, and 24 months after the last cycle of therapy if no progressive disease. Neck CT can be omitted at the discretion of the investigator if there was no involvement at baseline

If the patient is unable to follow up with the local site in person, virtual visits may be used to capture applicable procedures during long-term follow up only. If a virtual visit is completed in follow up every attempt should be made to complete the required assessments listed above, though if they are not completed it will not be considered a protocol deviation.

Patients who have progressive disease or start a new treatment are not required come in for clinical follow ups. These patients can be contacted over the phone by the study personnel to obtain the following information

- Disease status
- Adverse event evaluation only if patients have residual persistent symptoms related to BV treatment
- Current lymphoma treatment

11.4 Calendar

Screening procedures including scans are to be conducted within 28 days to administration of protocol therapy unless otherwise noted.

Study Calendar

| Tasks | Baseline/screening Day -28 to 1 | | Cycle 1 day 1 | | Cycle 2 -17 Day 1±3days | | Cycle 4 and 10 Day 15+5days | | Cycle 18 and beyond; Day 1 ±3days | | EOT Day 30-45 post last cycle | | Long term follow up ^m | | | |
|---|------------------------------------|----------------|---------------|---|-------------------------|---|-----------------------------|----------------|-----------------------------------|----------------|-------------------------------|----------------|----------------------------------|----------------|-----------|----------------|
| | | | | | | | | | | | | | 6 months | 12 months | 24 months | 36 months |
| Informed consent | x | | | | | | | | | | | | | | | |
| Inclusion/exclusion | x | | | | | | | | | | | | | | | |
| Medical history | x | | | | | | | | | | | | | | | |
| Physical exam | x | x | x | | | x | | x | | x | | x | | x | | x |
| CD30 status ^e | x | | | | | | | | | | | | | | | |
| HTLV-1 status | x | | | | | | | | | | | | | | | |
| IPI score | x | | | | | | | | | | | | | | | |
| PIT score | x | | | | | | | | | | | | | | | |
| ECHO | x | | | | | | | | | | | | | | | |
| EKG | x | | | | | | | | | | | | | | | |
| Vital signs, Height & weight | x ^l | x | x | | | x | | x | | x | | x | | x | | x |
| CBC with differential | x | x ^k | x | | | x | | x | | x | | x | | x | | x |
| Serum chemistry | x | x ^k | x | | | x | | x | | x | | x | | x | | x |
| LDH | x | x ^k | | | | | | x | | x | | x | | x | | x |
| Uric, Phosphorous | x | x ^k | | | | | | | | | | | | | | |
| Pregnancy test | | x ^c | | | | | | x | | | | | | | | |
| ECOG performance status | x | x | x | | | x | | x | | x | | x | | x | | x |
| Conmeds | x | x | x | | | x | | x | | | | | | | | |
| AE assessment | | | x | | | x | | x | | x ⁱ | | x ⁱ | | x ⁱ | | x ⁱ |
| Tumor tissue ^f | x | | | | | | | | | | | | | | | |
| CT neck/chest/abdomen/ Pelvis ^{a, h} | x ^j | | | x | | | | x | | x ^d | | x ^d | | x ^d | | |
| BM aspiration and biopsy | x ^g | | | | | | | x ^b | | | | | | | | |
| PET scan | x | | | | | | | x | | | | | | | | |
| Brentuximab Vedotin | | x | x | | | x | | | | | | | | | | |

- a. Neck CT can be omitted at the discretion of the investigator if there was no involvement at baseline. A +5-day window for scans during Cycle 4 and Cycle 10 is acceptable.
- b. Bone marrow biopsy only if positive prior to start of the study drug
- c. Pregnancy test to be done within 72 hours of starting the study drug

- d. Restaging CT scans not required if disease has progressed
- e. CD30 status to be assessed by the site enrolling the patient
- f. Tumor biopsy slides should be sent to CCF for correlative studies within 4 weeks of the start of the treatment
- g. Bone marrow biopsy only if evidence of involvement previously, and/or suspicion of involvement at the time of current relapse.
- h. For Cycles 18 and beyond, scans are to be done every six months +/- two weeks.
- i. Only adverse events attributed to the study drug
- j. CT neck can be omitted at baseline if the investigator feels there is no or low suspicion for involvement
- k. These labs do not need repeated on C1D1 if they were performed at baseline within 72 hours of start of study treatment
- l. Height is only required at screening.
- m. Long term follow up visits may be completed via virtual visit if necessary. Every attempt should be made to complete the assessments although if they are not completed this is not considered a protocol deviation.

12.0 MEASUREMENT OF EFFECT

12.1 Antitumor Effect

Response will be assessed using CT scans according to the revised Cheson Criteria [1]. Please see section 11.4 for the schedule of the imaging studies. Patients will have pre-treatment and end of treatment FDG-PET and/or CT to monitor their response to treatment. Interim response will be assessed after cycle 4 and 10 using CT scans. During follow up patients will have CT scans done at 6, 12, and 24 months after the last cycle of therapy.

All patients will be evaluable for toxicity from the time of their first treatment with Brentuximab Vedotin

The following guidelines are to be used for establishing tumor measurements at baseline and for subsequent comparison:

- The six largest dominant nodes or extranodal masses must be identified at baseline.
- If there are 6 or fewer nodes and extranodal masses, all must be listed as dominant.

If there are more than 6 involved nodes or extranodal masses, the 6 largest dominant nodes or extranodal masses should be selected according to the following features:

- nodes should be clearly measurable in at least two perpendicular measurements
- nodes should be from as disparate regions of the body as possible
- nodes should include mediastinal and retroperitoneal areas of disease whenever these sites are involved.
- Measurements for all dominant nodes and extranodal masses will be reported at baseline. Measurements on non-dominant nodes are not required. The lymph nodes or extranodal masses selected for measurement should be measured in two perpendicular diameters, one of which is the longest perpendicular diameter. The lymph nodes should be measured in centimeters to the nearest one tenth of a centimeter (e.g. 2.0 cm, 2.1cm, 2.2 cm, etc.)
- The two measured diameters of each lymph node site or extranodal mass should be multiplied giving a product for each nodal site or extranodal mass. The

product of each nodal site should be added, yielding the sum of products of the diameters (SPD). The SPD will be used in determining the definition of response for those who have less than a complete response.

12.2 Definitions

12.2.1 Primary Endpoint

12.2.1.1 Overall Response Rate

The primary objective is to evaluate overall response rate (ORR). Overall response rate will be estimated by the total number of patients who achieve a CR and PR divided by the total number of evaluable patients. Response will be assessed using CT scans according to the revised Cheson criteria [1].

- CR is defined as complete resolution of all clinically detectable disease and disease related symptoms that were present prior to therapy
- PR is defined as at least 50% decrease in sum of the product of the diameters (SPD) of up to six of the largest dominant nodes or nodal masses

Patients should have completed at least 1 cycle of treatment to be evaluable for ORR.

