3.1 Number of Subjects

We plan to enroll up to 31 patients to obtain 28 evaluable subjects to assess ORR.

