6.0 TREATMENT PLAN

6.1 Brentuximab Vedotin Administration

Subjects will receive Brentuximab Vedotin 1.8 mg/kg intravenously (IV) once every 3 weeks.

The treatment will be continued until disease progression, unacceptable toxicity, stem cell transplantation or at physician discretion. If a patient has completed 17 cycles, the treating physician can determine if to continue or discontinue treatment in event there is no disease progression or unacceptable toxicity.

CASE 1415

Protocol Version Date: 07/06/2021

Appropriate dose modifications for Brentuximab Vedotin are described in Section 7.0.

For reported adverse events see section 8.0 and potential risks of Brentuximab Vedotin are described in Section 9.0.

No investigational or commercial agents or therapies other than those described below may be administered with the intent to treat the patient's malignancy.

Table 1

| Treatment Regimen | | | | | |
|--------------------------|-----------------------------------|-------------|--------------------|---------------------|---------------------|
| Agent | Pre-medicate / Precautions | Dose | Route | Schedule | Cycle Length |
| Brentuximab Vedotin | None (please see below) | 1.8 mg/kg | IV over 30 minutes | Day 1 of each cycle | 21 days |

All scheduled treatment visits will have a ± 3 -day window due to unanticipated or unavoidable scheduling conflicts except for cycle 1, day 1.

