12.2.2 Secondary Endpoints

12.2.2.1 Complete Response

CR is defined as complete resolution of all clinically detectable disease and disease related symptoms that were present prior to therapy. A post-treatment residual mass of any size is permitted as long as it is PET negative. CR rate will be calculated by dividing the total number of patients who have achieved a complete response by the total number of evaluable patients.

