14.0 STATISTICAL CONSIDERATIONS

Please refer section 12.2 for endpoint definitions. The primary objective is to evaluate overall response rate. For this patient population, response of 15% or less is unacceptable and 35% or more is promising. Twenty-eight evaluable patients will be accrued; if 8 or more patients respond, then the regimen will be considered promising. The significance level of this one-sided test is 5%, and the power is 82%.

Other end points analyzed are CR, PFS, OS, DOR, and TTF. ORR and CR will be estimated using exact 95% confidence intervals. PFS and OS will be estimated using the Kaplan-Meier method. DOR and TTF will be estimated using standard descriptive statistics such as median and range, or mean and standard deviation.

McNemar's test will be used to compare incidence of CD30 positivity via IHC with multi- spectral imaging and RT-PCR to see if different methods result in different findings.

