15.0 Sample Size

We plan to enroll 31 patients, allowing for 10% ineligibility, to obtain 28 patients evaluable for primary end point, overall response rate.

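### The response-rate denominator is limited to patients who completed a cycle, a term left undefined; if it means reaching day 21, early losses drop out and the ORR is modestly inflated

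*Combined protocol and SAP*

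**What the plan says.** Section 12.2.1.1 defines the ORR as CR plus PR over evaluable patients, with the condition "Patients should have completed at least 1 cycle of treatment to be evaluable for ORR". Section 12.2.2.1 uses the same denominator for the CR rate, "dividing the total number of patients who have achieved a complete response by the total number of evaluable patients". Section 14.0 applies the decision rule to that population: "Twenty-eight evaluable patients will be accrued; if 8 or more patients respond, then the regimen will be considered promising".

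Treatment is one infusion per cycle. Section 6.1 states "Subjects will receive Brentuximab Vedotin 1.8 mg/kg intravenously (IV) once every 3 weeks", and Table 1 places the dose on day 1 of a 21-day cycle. The first on-treatment scan is in cycle 4 (section 11.1.6, "Cycle #4 and #10 day 15 ± 5 days"). Safety has a different entry point, in section 12.1: "All patients will be evaluable for toxicity from the time of their first treatment with Brentuximab Vedotin".

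On numbers, section 15.0 says "We plan to enroll 31 patients, allowing for 10% ineligibility, to obtain 28 patients evaluable for primary end point, overall response rate" and section 3.1 says "We plan to enroll up to 31 patients to obtain 28 evaluable subjects to assess ORR".

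**The concern.** A cycle of one infusion followed by about three weeks without treatment can be complete in two senses: the dose was given, or the cycle ran its course. The protocol does not choose. Section 12.1 ties toxicity evaluability to the first treatment, while section 12.2.1.1 uses other words for ORR. That suggests the stricter sense but does not settle it.

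On the stricter sense, membership of the primary analysis set depends on what happens after dosing. A treated patient who dies or leaves the study before day 21 drops out of numerator and denominator alike. Such a patient has no scheduled on-treatment scan and is almost always a non-responder. Nothing in sections 12 or 14 counts these patients as failures or asks for an all-treated ORR. The reported ORR and CR rate would then overstate the effect in treated patients.

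There is a second effect. The three places between 28 and 31 are allotted to ineligibility alone, so cycle 1 losses would draw on an allowance not sized for them.

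**Working it through.** **Inputs.** From section 14.0: unacceptable rate 15%, promising rate 35%, n = 28, success at 8 or more responders, one-sided 5%, power 82%. From sections 15.0 and 3.1: 31 enrolled, 10% ineligible, cap of 31. Assumed, because the documents give no figure: a fraction f of treated patients lost in cycle 1, all non-responders, with f = 3%, 5% or 9.7% (3/31, equal to all the spare places).

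**The plan's own figures.** P(X ≥ 8 | n = 28, p = 0.15) = 0.0486 and P(X ≥ 8 | n = 28, p = 0.35) = 0.8179. The stated 5% and 82% reproduce.

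**Inflation of the ORR.** The rate among completers is p/(1 − f).

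| f | true 15% appears as | true 35% appears as |
|---|---|---|
| 3% | 0.15/0.97 = 15.5% | 0.35/0.97 = 36.1% |
| 5% | 0.15/0.95 = 15.8% | 0.35/0.95 = 36.8% |
| 9.7% | 0.15 × 31/28 = 16.6% | 0.35 × 31/28 = 38.8% |

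**At the boundary.** 8/28 = 28.6% (exact 95% CI 13.2% to 48.7%). Adding back one, two or three excluded non-responders gives 8/29 = 27.6%, 8/30 = 26.7% and 8/31 = 25.8%. The exact one-sided p-value for 8 responders against 15% is 0.0486 at n = 28 and 0.0586, 0.0698 and 0.0822 at n = 29, 30 and 31. A single exclusion moves it across 5%.

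**Type I error when 28 evaluable patients are always reached.** P(X ≥ 8 | 28, 0.15/(1 − f)) = 5.7%, 6.3% and 8.0%.

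**Type I error and power under the cap.** The number analysed is min(28, Bin(31, q)), with the cut-off kept at 8 whatever that number is. For the end-of-cycle rule q = 0.9(1 − f); for an all-eligible-dosed rule q = 0.9.

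| | f = 3% | f = 5% | f = 9.7% |
|---|---|---|---|
| P(28 reached), end-of-cycle rule | 43% | 32% | 14% |
| Type I error, end-of-cycle rule (15% in all treated) | 4.5% | 4.7% | 4.8% |
| Power, end-of-cycle rule (35% in all treated) | 79.9% | 80.3% | 80.6% |
| Power, end-of-cycle rule (35% in completers only) | 76.6% | 74.6% | 69.0% |
| Power, all-dosed rule (35% in completers only) | 75.6% | 73.2% | 66.9% |

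Under the all-dosed rule 28 patients are reached in 62% of trials, the type I error is 4.3%, and power is 79.0% if 35% holds in all treated patients.

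**The case against.** The strongest reply is that only an undefined word has been shown. If completing a cycle means receiving its infusion, every treated patient is counted and there is nothing to correct. The protocol also times end-of-treatment and follow-up visits from the last cycle of therapy (sections 6.7.2, 11.2 and 11.3), which fits treating a cycle as its dose. This stands: the bias is conditional on the end-of-cycle reading.

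Even on that reading the affected group is small. A patient who progresses but stays on study to day 21 remains in the denominator. One who stops early for toxicity has an end-of-treatment scan under section 11.2 and could be a responder. The inflation is 0.5 to 1.6 points at 15% and 1.1 to 3.8 points at 35%, against a confidence interval about 35 points wide, and the type I error stays under 5% in the cap model. PFS, OS and TTF all run from enrollment with death as an event, so early deaths are visible there. All of this stands, and it is why the effect is called modest and placed in the estimate rather than in the error rate.

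The accrual percentages are softer. They assume a hard cap, whereas the Schema gives 31 as approximate. They apply a cut-off of 8 below n = 28, which the plan does not state. At f = 9.7% a loss equal to all the spare places is added to 10% ineligibility. The 62% starting point comes from ineligibility alone.

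None of this answers the main point. The text permits a primary population selected on post-dose outcome, and it neither rules that reading out nor supplies an all-treated figure beside it.

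**Conclusion.** The concern holds and should be fixed. Whether a bias exists depends on the end-of-cycle reading, and its size rests on an assumed cycle 1 loss of 3% to 9.7%, all non-responders. On those terms the ORR is overstated by roughly 0.5 to 4 percentage points, and a boundary result of 28.6% would be 25.8% to 27.6% in treated patients. The CR rate is biased in the same direction. Excess type I error is not the main harm: it reaches 5.7% to 8.0% only if 28 evaluable patients are always obtained. On the infusion-received reading the problem all but disappears, but the protocol would still need to say so.

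**What to change.** Define evaluable for ORR and CR rate as all eligible patients who receive any brentuximab vedotin. Count those with no post-baseline response assessment as non-responders; this also settles the status of patients lost after cycle 1 but before the cycle 4 scan. Keep n = 28 and the cut-off of 8 in that population. State what completing one cycle means, and report the completed-cycle ORR as a supportive analysis.

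The cost is an amendment to the primary analysis population, with no added patients and possibly a slightly lower reported ORR. The stated 82% power still applies at n = 28 if 35% is the rate among dosed patients. If 35% holds only among patients who complete cycle 1, power at n = 28 is P(X ≥ 8 | 28, 0.35(1 − f)) = 78.6%, 76.2% or 70.2%; section 14.0 should say which population the 35% refers to. Compared like for like under the cap, the change costs 1.0 to 2.1 points of power if 35% holds in completers only, and 0.9 to 1.6 points if it holds in all treated patients. If the sponsor already means dosed, the amendment only records that.

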12.2.2 Secondary Endpoints

12.2.2.1 Complete Response

CR is defined as complete resolution of all clinically detectable disease and disease related symptoms that were present prior to therapy. A post-treatment residual mass of any size is permitted as long as it is PET negative. CR rate will be calculated by dividing the total number of patients who have achieved a complete response by the total number of evaluable patients.

12.2.2.2 Progression Free Survival

Progression-free survival (PFS) is defined as the time from enrollment into the study to disease progression or death due to any cause. The distribution of PFS will be estimated using the Kaplan-Meier method. Disease progression may be defined as the date of documentation of a new lesion or enlargement of a previous lesion, or the date of the scheduled clinic visit immediately after radiologic assessment has been completed. For a patient who is alive without progression at the end of study follow-up, observation of PFS is censored on the date of last contact.

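### Section 12.2.2.2 allows two dates for the same progression with no rule for choosing; the visit date is never earlier than the scan date, so PFS and DOR can be inconsistent and too long

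*Combined protocol and SAP*

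**What the plan says.** Section 12.2.2.2 gives PFS as "defined as the time from enrollment into the study to disease progression or death due to any cause", estimated by Kaplan-Meier. It then offers two dates for the progression event. The first: "Disease progression may be defined as the date of documentation of a new lesion or enlargement of a previous lesion". The second: "or the date of the scheduled clinic visit immediately after radiologic assessment has been completed". The wording is permissive, and no order of preference follows.

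No other section settles the choice. Section 12.1 describes imaging and measurement, and section 12.3 assigns response review to the treating investigator at each site. Section 14.0 names the estimation methods, and Appendix 2 gives response categories without dates. Section 12.2.2.4 ends DOR at progression or death and adds no dating rule.

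The schedule that fixes the second date is in section 11:

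- On treatment, visits fall on day 1 of each 21-day cycle, ±3 days (11.1.5). Scans are set at "Cycle #4 and #10 day 15 ± 5 days" (11.1.6); the calendar in 11.4 gives day 15 with a +5-day window.
- At end of treatment the visit is 30 to 45 days after the last cycle, and CT is paired with a "PET scan to be done between 30-45 days after the last cycle of therapy" (11.2).
- Later: "The follow up visits will be done at 6, 12, 24 and 36 months after the last cycle of therapy" (11.3), with CT at 6, 12 and 24 months.
- After progression: "Patients who have progressive disease or start a new treatment are not required come in for clinical follow ups" (11.3); telephone contact is enough.

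**The concern.** A time-to-event endpoint needs one event date per patient. Here two people who both follow the protocol can record different PFS times for identical patients. The plan does not say who assigns the date.

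The discrepancy has a direction. A visit held after the scan is on or after the scan date, so mixing the two dates can only leave PFS and DOR unchanged or lengthen them. The lengthening also depends on when progression is found, because visits are weeks apart on treatment and months apart afterwards.

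The second date may also be missing. Section 11.3 releases patients with progression from the follow-up visits that would supply it, so the visit option could not be applied to every patient even if everyone preferred it.

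**Working it through.** **The plan's own figure.** The plan states no figure for PFS or DOR. Its only design figure is for response rate (section 14.0: 8 or more of 28, 15% versus 35%, one-sided 5%, power 82%). Exact binomial: P(X ≥ 8 | n = 28, p = 0.15) = 4.86% and P(X ≥ 8 | n = 28, p = 0.35) = 81.8%, in agreement. Neither uses a progression date.

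**Formula.** Lag = date of the next scheduled visit − date of the scan. One month = 365.25/12 = 30.44 days. The documentation date is taken to be the scan date.

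**On treatment.**

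- Cycle 4 day 15 is study day 3×21 + 15 = 78. Cycle 5 day 1 is 4×21 + 1 = 85. Lag 7 days. Cycle 10 gives the same lag.
- With the scan on day 15 to 20 and the visit on its nominal date (cycle day 22): 22 − 20 = 2 to 22 − 15 = 7 days.
- With the visit 3 days late (cycle day 25): at most 25 − 15 = 10 days on the calendar's scan window, or 25 − 10 = 15 days on the ±5 window in 11.1.6.
- With a 3-week hold as well: at most 25 + 21 − 10 = 36 days.
- If the cycle 4 scan shows progression, treatment stops (6.1) and the cycle 5 visit may not occur. The next scheduled visit is then end of treatment. Assuming the 30 to 45 days run from cycle 4 day 1 (day 3×21 + 1 = 64), it falls on day 94 to 109: a lag of 16 to 31 days from day 78.
- From cycle 18 on, visits stay 21 days apart: at most 21 days, or 21 + 3 + 3 = 27 with both windows.

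**Off treatment.** Sections 11.2 and 11.3 list each protocol scan with its matching visit but do not fix their order.

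| Situation | Lag |
|---|---|
| End-of-treatment scan on or before its own visit | 0 to 45 − 30 = 15 days |
| Scan on or just before the 6-, 12- or 24-month visit | 0 to a few days |
| End-of-treatment scan after its own visit; next visit at month 6 | 182.6 − 45 = 138 to 182.6 − 30 = 153 days (4.5 to 5.0 months) |
| Scan after the 6-month visit, or unscheduled between months 6 and 12 | up to 6 months |
| Same, between months 12 and 24 or 24 and 36 | up to 12 months |

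The first two rows are the ordinary case. The last three are upper limits.

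**Effect on one patient at the upper limit.** Assume the last dose is on cycle 4 day 1 without delay, time runs from cycle 1 day 1 as a stand-in for enrollment, and progression is first seen on an end-of-treatment scan done after its visit. By scan date, PFS = (63 + 30)/30.44 to (63 + 45)/30.44 = 3.1 to 3.5 months. By the next scheduled visit, PFS = (63 + 182.6)/30.44 = 8.1 months.

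**The case against.** The best defence is that the lag is normally small. Off treatment, the protocol pairs each scan with a visit. On treatment, visits are 21 days apart, and a patient treated until progression will usually have it found under that schedule. A lag of months needs a scan that follows its own visit or was never scheduled, and the plan gives no basis for saying how often that happens. This stands, and it is why the larger figures are given only as conditional limits. A reader might infer that off-treatment PFS is routinely overstated by months; the schedule does not support that.

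Nor does the visit option always move progression later. If scan and visit fall on the same day, the two dates coincide.

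It can also be said that the missing visit and the long lag pull against each other: if no visit takes place, the documentation date is the natural fallback and no bias arises. That is fair for the individual patient. It does not rescue the rule, because some patients would then be dated one way and some the other, according to whether they attended an optional visit.

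Finally, the phrase may have been meant as a prompt visit to discuss the scan. The text says a scheduled visit, however, and the schedule contains no such extra visit.

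**Conclusion.** The point holds. Section 12.2.2.2 gives two dates for one event and no way to choose, so PFS and DOR can be inconsistent between patients, and any bias is upward. The usual size is about 1 week for an on-treatment scan and 0 to 15 days off treatment. The conditional upper limit is 138 to 153 days when the end-of-treatment scan follows its own visit, and up to 6 or 12 months only for an unscheduled scan or one done after its matching follow-up visit.

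These sizes rest on the protocol schedule, on reading the documentation date as the scan date, and on 30.44-day months. How many patients would be affected cannot be estimated from the documents.

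Two wider inferences are not supported. The primary analysis is untouched: the 8-of-28 rule and its power depend on response, not on the date of progression. TTF is also outside the point, because section 12.2.2.5 ends it when treatment is discontinued. PFS and DOR are secondary and descriptive, so this should be corrected but does not threaten the trial's main conclusion.

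**What to change.** Replace the dating sentence in section 12.2.2.2 with: *The date of progression is the date of the first scan (or clinical assessment, if no scan is done) that documents a new or enlarged lesion.* Delete the clinic-visit alternative. State in section 12.2.2.4 that DOR uses the same date. Do not extend the rule to TTF, where it would conflict with section 12.2.2.5.

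The cost is one sentence and a cross-reference. Scan dates should already be in the source records. No visit, scan, sample size or primary analysis changes. PFS and DOR may look slightly shorter than they would with visit dates.
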